1.3 Schedule of Activities

Table 1 Period 1 (Weeks -2 to 12)

At the discretion of the Investigator, and with the exception of Weeks 8 and 12 (which must be conducted at the site), study visits for patients who have undetectable BK plasma viral load at 2 or more consecutive assessments at least 2 weeks apart after 3 doses may be conducted by a Sponsor-approved home health vendor in conjunction with a Sponsor-approved telehealth provider. These visits may be conducted via video or telephone call.

Study Week	Weeks -2 to -1	Day 1	Week 1	Week 2	Week 4	Week 6	Week 8	Week 10	Week 12
Study Day	-14 to -1	1 ^[1]	8	15	29	43	57	71	85
Visit Window (Days)	NA	NA	±2	±3	±3	±3	±3	±3	±3
Study Procedures									
Informed consent ^[2]	X								
I/E criteria	X	X							
Demographics	X								
Medical history	X								
Prior & concomitant medications	X	X	X	X	X	X	X	X	X
Adverse events ^[3]	X	X	X	X	X	X	X	X	X
Complete physical examination ^[4]	X	X							X
Targeted physical examination ^[4]			X	X	X	X	X	X	
Weight and height ^[5]	X	X			X		X		X
Vital signs ^[6]	X	X	X	X	X	X	X	X	X
12-lead ECG ^[7]	X	X ^[7]		X ^[7]					
Documentation of HLA typing ^[8]	X								
Clinical labs ^[9]	X	X		X	X	X	X	X	X
Testing for HIV, HCV, and HBV ^[22]	X								
BKV plasma viral load ^[10,11]	X	X		X	X	X	X	X	X
Urine for biomarker ^[12]		X			X		X		X
AdV, CMV, JCV, HHV-6 plasma, and EBV viral load ^[10]		X			X		X		X
Pregnancy test	X ^[13]	X ^[14]			X ^[14]		X ^[14]		X ^[14]
FSH ^[15]	X								
Randomization ^[16]		X							
Provide patient cards		X							

Study Week	Weeks -2 to -1	Day 1	Week 1	Week 2	Week 4	Week 6	Week 8	Week 10	Week 12
Study Day	-14 to -1	1 ^[1]	8	15	29	43	57	71	85
Visit Window (Days)	NA	NA	±2	±3	±3	±3	±3	±3	±3
Study treatment administration ^[17]		X	X	X	X	X	X	X	X
Post infusion monitoring ^[18]		X	X	X	X	X	X	X	X
Banked PBMCs for virus specific immunity ^[19]	X			X	X	X	X		X
Blood for donor DNA ^[20]					X				X
Kidney biopsy pathologic specimens for review (if clinically indicated) ^[23]	X	X	X	X	X	X	X	X	X
Donor-specific antibodies ^[24]		X							X

1. Unless noted otherwise, the Day 1 procedures must be performed within 96 hours of randomization and prior to study treatment administration.
2. Prior to conducting any study-related activities, written informed consent to participate in the study must be provided by the patient.
3. Adverse events will be monitored and documented from randomization through Week 24 in all patients.

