Table 2 Period 2 (Weeks 14 to 24; Follow-Up Period)

At the discretion of the Investigator, all study visits during Period 2 may be conducted by a Sponsor-approved home health vendor in conjunction with a Sponsor-approved telehealth provider. These visits may be conducted via video or telephone call.

Study Week	Week 14	Week 16	Week 18	Week 20	Week 22	Week 24/ET ^[1]
Study Day	99	113	127	141	155	169
Visit Window (Days)	±7 Days					
Study Procedures						
Prior & concomitant medications	X	X	X	X	X	X
Adverse events ^[3]	X	X	X	X	X	X
Targeted physical examination ^[4]	X	X	X	X	X	X
Weight ^[5]		X		X		X
Vital signs ^[6]	X	X	X	X	X	X
12-lead ECG ^[7]						X
Clinical labs ^[8]		X		X		X
BKV plasma viral load ^[10,11]	X	X	X	X	X	X
AdV, CMV, JCV, EBV, and HHV-6 plasma viral load ^[10]			X			X
Banked PBMCs for virus-specific immunity ^[19]		X		X		X
Blood for donor DNA ^[20]						X
Obtain any clinically indicated kidney biopsy pathologic specimens for review ^[23]	X	X	X	X	X	X
Donor-specific antibodies ^[24]						X

See footnotes and abbreviations following [Table 1](#).

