6.6 Continued Access to Study Treatment after the End of the Study

No further treatment will be provided after the last dose of PSL (or placebo) after Week 12. However, patients will continue in the study for evaluation of safety, efficacy, and other endpoints for an additional 12 weeks.

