7 DISCONTINUATION OF STUDY TREATMENT AND PATIENT DISCONTINUATION/WITHDRAWAL

7.1 Discontinuation of Study Treatment

The following criteria do not necessitate withdrawal from the study, but do render the patient ineligible to receive any additional infusions of study treatment:

1. Development of \geq Grade 1 acute GVHD within 6 weeks, or a Grade 3 to 4 non-hematologic AE within 4 weeks from last PSL dose that is considered related to study treatment administration. If this occurs, the patient's toxicities will be followed until resolution or until the patient's participation in the study ends.
2. Receipt of any other hematopoietic stem cell product.
3. Receipt of therapy for new malignancy.
4. Occurrence of Grade 3 or 4 CRS. If this occurs, the patient's toxicities will be followed until resolution or until the patient's participation in the study ends.
5. Requirement for prohibited concomitant medication
6. Pregnancy

If any of the above criteria are met, every effort should be made to keep the patient in the study and continue follow-up.

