8.2.4 Clinical Safety Laboratory Assessments

- See Appendix 2 ([Section 10.2](#)) for the list of clinical laboratory tests to be performed and the SoA ([Section 1.3](#)) for the timing and frequency.
- The Investigator must review the laboratory report, document this review, and record any clinically significant changes occurring during the study as an AE. The laboratory reports must be filed with the source documents.
- Abnormal laboratory findings associated with the underlying disease are not considered clinically significant unless judged by the Investigator to be more severe than expected for the patient's condition.
- All laboratory tests with values considered clinically significantly abnormal during participation in the study or within 28 days after the last dose of study treatment should be repeated until the values return to normal or baseline or are no longer considered clinically significant by the Investigator or Medical Monitor.
 - If clinically significant values do not return to normal/baseline within a period of time judged reasonable by the Investigator, the etiology should be identified, and the Sponsor notified.
 - All protocol-required laboratory tests, as defined in Appendix 2 ([Section 10.2](#)), must be conducted in accordance with the laboratory manual and the SoA ([Section 1.3](#)).
 - If laboratory values from non-protocol specified laboratory tests performed at the institution's local laboratory require a change in patient management or are considered clinically significant by the Investigator (eg, SAE or AE or dose modification), then the results must be recorded.

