8.3.7 Adverse Events of Special Interest

Adverse events of special interest (AESI) include infusion-related AEs, GVHD, and CRS. Grading criteria for GVHD and CRS can be found in Appendix 5 ([Section 10.5](#)) and Appendix 6 ([Section 10.6](#)), respectively. These AESIs will be reviewed by the DSMB as per the DSMB Charter.

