9.5.1.2 Stopping Criteria for the Study

Randomization into the study will be halted if 3 patients experience SAEs that meet the following criteria:

- \geq CTCAE Grade 3,
- Considered related by the Investigator,
- Occur during Period 1 following the initial dose, AND
- Cannot be reasonably attributed to the patient's underlying disease, other medical condition, or concomitant medications.

If this occurs, randomization will not resume until the DSMB has thoroughly reviewed all safety data to date and concluded that it is safe for the study to continue.

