10.1.5 Committee Structure

10.1.5.1 Data Safety and Monitoring Board

An independent DSMB will be convened for this study to routinely monitor patient safety and evaluate prespecified interim analyses to stop the study or either arm early. The DSMB will receive summary reports of all unexpected SAEs. A DSMB charter, detailing all aspects of the DSMB's composition, scope of review, and procedures will be provided in a separate document. In addition, the DSMB will review safety data after the first 3 patients enrolled have received their 3rd dose.

An unblinded statistician will be assigned to the DSMB. This statistician will not be involved in any aspects of study conduct outside of the DSMB, and their role will be defined in the DSMB charter.

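### The automatic halt on randomization stops counting serious related events at the end of Period 1, whose final visit is also the last infusion, so it gives little or no cover after the final doses

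*Protocol*

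**What the plan says.** Protocol 9.5.1.2 halts randomization once three patients have an SAE that is CTCAE Grade 3 or higher, judged related by the investigator and not reasonably explained by another cause. The event must also "Occur during Period 1 following the initial dose, AND". Randomization then stays closed until the DSMB has reviewed all safety data and judged it safe to continue.

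Table 1 (Section 1.3) defines Period 1 as Weeks -2 to 12 and schedules infusions on Days 1, 8, 15, 29, 43, 57, 71 and 85. Section 6.6 confirms that dosing ends there: "No further treatment will be provided after the last dose of PSL (or placebo) after Week 12". Table 2 covers "Period 2 (Weeks 14 to 24; Follow-Up Period"), has no dosing, and starts with a visit on Day 99.

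Other sections look further past a dose:
- Section 7.1 ends a patient's dosing for a Grade 3 to 4 non-hematologic event "within 4 weeks from last PSL dose that is considered related to study treatment administration", and for acute GVHD within 6 weeks.
- Section 8.2.4 says clinically significant laboratory abnormalities during participation or "within 28 days after the last dose of study treatment should be repeated".
- Section 1.3, footnote 3: "Adverse events will be monitored and documented from randomization through Week 24 in all patients".

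On oversight, Section 10.1.5.1 says "The DSMB will receive summary reports of all unexpected SAEs", and Section 8.3.7 says of the events of special interest, "These AESIs will be reviewed by the DSMB as per the DSMB Charter". Neither statement is limited to Period 1. Nothing in the protocol or SAP extends the automatic halt into Period 2.

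**The concern.** A rule meant to catch product toxicity should cover the time in which the sponsor expects that toxicity to appear. Here counting ends on the day of the final infusion, apart from events later that same day. Patients who reach Week 12 on the 14-day schedule have had the most cells, and their events drop out of the count at that point.

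Three related serious events in the weeks after the last infusions would therefore not pause randomization automatically, while new patients might still be entering. Safety is the primary objective, and Section 4.3 acknowledges that the product had not yet been used in solid organ transplant recipients.

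**Working it through.** **Check of the calendar.** Week w falls on Day 7w + 1, so Week 12 = Day 85, Week 14 = Day 99 and Week 24 = Day 169. All three match the schedule.

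**Where Period 1 ends.** The protocol does not say to which period Days 86 to 98 belong. Sections 1.1 and 4.1 describe 2 weeks of screening, 12 of treatment and 12 of follow-up. Since (169 − 85)/7 = 12, Day 85 fits best. The generous alternative is Day 98, the day before the nominal Week 14 visit. Both are shown.

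**Cover after each infusion.** Days covered = min(window, end of Period 1 − infusion day).

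| Infusion day | 28-day window, end Day 85 | 42-day window, end Day 85 | 28-day window, end Day 98 | 42-day window, end Day 98 |
|---|---|---|---|---|
| 1 to 43 | 28 | 42 | 28 | 42 |
| 57 | 28 | 28 | 28 | 41 |
| 71 | 14 | 14 | 27 | 27 |
| 85 | 0 | 0 | 13 | 13 |

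On either reading, 6 of 8 infusions have the full 4-week window inside Period 1 and 5 of 8 have the full 6-week window. The gap belongs to the last doses.

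**Share of risk days outside the rule.** Risk days run from Day 1 to last PSL dose + window. Days outside = that end day − end of Period 1.

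| Last PSL dose | Window | Outside, end Day 85 | Outside, end Day 98 |
|---|---|---|---|
| Day 85 | 28 days (to Day 113) | 28/113 = 25% | 15/113 = 13% |
| Day 85 | 42 days (to Day 127) | 42/127 = 33% | 29/127 = 23% |
| Day 71 | 28 days (to Day 99) | 14/99 = 14% | 1/99 = 1% |
| Day 71 | 42 days (to Day 113) | 28/113 = 25% | 15/113 = 13% |

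SAP 2.2.3 gives 14- and 28-day intervals after three weekly doses. The exact PSL days are redacted, so Day 71 as the last active dose in the 28-day arm is an assumption. Patients who stop early have smaller shares, down to zero.

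**Would a pause still protect anyone?** Section 4.1 expects about 12 months of enrollment. Assuming uniform accrual, the share of patients who finish the window before randomization closes is:
- 4 weeks: (365 − 84 − 28)/365 = 0.693
- 6 weeks: (365 − 84 − 42)/365 = 0.655

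In the 14-day arm of 20 that is 13.9 and 13.1 patients. Both are upper bounds, because they allow nothing for early stopping or withdrawal.

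**Illustration on assumed rates.** The plan gives no operating characteristics for this rule, so there is none to reproduce. With 40 PSL patients, per-patient risk p of a qualifying event and a fraction f of events falling after Period 1, the chance of at least three counted patients is P(X ≥ 3), X ~ Binomial(40, p(1 − f)):

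| p | f = 0 | f = 20% | f = 40% |
|---|---|---|---|
| 2% | 0.046 | 0.026 | 0.012 |
| 5% | 0.323 | 0.214 | 0.118 |
| 10% | 0.777 | 0.631 | 0.433 |

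This ignores timing relative to the close of randomization, so it overstates the practical loss.

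**The case against.** Limiting an automatic pause to the treatment period is a defensible choice. Neither document calls 28 or 42 days the product's risk window. Section 7.1 decides whether one patient may be dosed again, and its 6-week part covers GVHD from Grade 1, most of which would never be a Grade 3 SAE. Section 8.2.4 only concerns repeat laboratory tests. Late events would also not go unseen. SAEs are reported within 24 hours throughout participation (8.3.1), unexpected serious reactions go to regulators within 7 or 15 days (8.3.4.1), the DSMB monitors safety routinely and may evaluate stopping (10.1.5.1), and the sponsor can end the study at any time (10.1.9). The largest shares apply only to patients given cells on Day 85.

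Much of this stands. There is no contradiction with 7.1, the shares are of days rather than risk, and oversight continues after Week 12. Two points do not carry. The benchmark does not rest on 7.1 alone: Section 2.3.2.2 describes 30 days of toxicity follow-up and 6 weeks for GVHD in the donor-derived T cell study, and 2.3.2.3 a 28-day safety follow-up for posoleucel itself. And none of the oversight provisions sets a count that closes randomization. The DSMB charter might, but it is not available, so it cannot be relied on.

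**Conclusion.** The concern holds. The only automatic study-level pause stated in these documents gives 0 of 28 days of cover after the Day 85 infusion, or 13 on the generous reading, and half cover (14 of 28) after Day 71. For a patient dosed with cells on Day 85, 25% (4-week window) or 33% (6-week window) of risk days fall outside it, or 13% and 23% if Period 1 runs to Day 98. Under uniform accrual, at most about 14 of the 20 patients in the 14-day arm would complete the uncovered 4 weeks while randomization is open.

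This is a misaligned design choice rather than an error, and no loss of detection can be quantified without a late-event rate. It is worth correcting because the rule protects new entrants in a first study in this population and the correction needs no extra data. Confidence is medium, given the redacted dosing days and the unseen charter.

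**What to change.** In Protocol 9.5.1.2, replace the Period 1 criterion with: *Occur from the initial dose through the Week 12 visit or 28 days (42 days for GVHD) after the last infusion of study treatment, whichever is later.*

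Counting from the last blinded infusion, PSL or placebo, lets the rule run without unblinding. The whichever-is-later clause matters: with a plain 28-day limit, a patient whose last infusion was Day 29 would stop counting on Day 57, losing 28 days of present cover (85 − 57). The wording also settles the Day 85 to 99 boundary; if the sponsor meant Period 1 to last until Day 98, that day should replace the Week 12 visit.

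No new visits or data are needed. Day 113 (Week 16) and Day 127 (Week 18) are existing visits, and adverse events are already collected to Week 24. The costs are a protocol amendment, which under 10.1.1 needs ethics approval and, if substantial, health authority approval, and a slightly higher chance of a pause for DSMB review.

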10 SUPPORTING DOCUMENTATION AND OPERATIONAL CONSIDERATIONS

10.1 Appendix 1: Regulatory, Ethical, and Study Oversight Considerations

10.1.1 Regulatory and Ethical Considerations

- This study will be conducted in accordance with the protocol and with the following:
 - Consensus ethical principles derived from international guidelines including the Declaration of Helsinki and Council for International Organizations of Medical Sciences (CIOMS) International Ethical Guidelines
 - Applicable ICH Good Clinical Practice (GCP) Guidelines
 - Applicable laws and regulations
- The protocol, protocol amendments, ICF, Investigator Brochure, and other relevant documents (eg, advertisements) must be submitted to an IRB/IEC by the Investigator and reviewed and approved by the IRB/IEC before the study is initiated.
- Any amendments to the protocol will require IRB/IEC approval before implementation of changes made to the study design, except for changes necessary to eliminate an immediate hazard to study patients.
- Protocols and any substantial amendments to the protocol will require health authority approval prior to initiation except for changes necessary to eliminate an immediate hazard to study patients.
- The Investigator will be responsible for the following:
 - Providing written summaries of the status of the study to the IRB/IEC annually or more frequently in accordance with the requirements, policies, and procedures established by the IRB/IEC
 - Notifying the IRB/IEC of SAEs or other significant safety findings as required by IRB/IEC procedures
 - Providing oversight of the conduct of the study at the site and adherence to requirements of 21 Code of Federal Regulations (CFR), ICH guidelines, the IRB/IEC, European regulation 536/2014 for clinical studies (if applicable), European Medical Device Regulation 2017/745 for clinical device research (if applicable), and all other applicable local regulations

10.1.2 Financial Disclosure

Investigators and sub-Investigators will provide the Sponsor with sufficient, accurate financial information as requested to allow the Sponsor to submit complete and accurate financial certification or disclosure statements to the appropriate regulatory authorities. Investigators are responsible for providing information on financial interests during the course of the study and for 1 year after completion of the study.

10.1.3 Informed Consent Process

- The Investigator or his/her representative will explain the nature of the study to the patient and answer all questions regarding the study.
- Patients must be informed that their participation is voluntary. Patients will be required to sign a statement of informed consent that meets the requirements of 21 CFR 50, local regulations, ICH guidelines, Health Insurance Portability and Accountability Act (HIPAA) requirements, where applicable, and the IRB/IEC or study center.
- The medical record must include a statement that written informed consent was obtained before the patient was enrolled in the study and the date the written consent was obtained. The authorized person obtaining the informed consent must also sign the ICF.
- Patients must be re-consented to the most current version of the ICF(s) during their participation in the study.
- A copy of the ICF(s) must be provided to the patient.

10.1.4 Data Protection

- Patients will be assigned a unique identifier by the Sponsor. Any patient records or datasets that are transferred to the Sponsor will contain the identifier only; patient names or any information which would make the patient identifiable will not be transferred.
- The patient must be informed that his/her personal study-related data will be used by the Sponsor in accordance with local data protection law. The level of disclosure must also be explained to the patient who will be required to give consent for their data to be used as described in the informed consent
- The patient must be informed that his/her medical records may be examined by Clinical Quality Assurance auditors or other authorized personnel appointed by the Sponsor, by appropriate IRB/IEC members, and by inspectors from regulatory authorities.

10.1.5 Committee Structure

10.1.5.1 Data Safety and Monitoring Board

An independent DSMB will be convened for this study to routinely monitor patient safety and evaluate prespecified interim analyses to stop the study or either arm early. The DSMB will receive summary reports of all unexpected SAEs. A DSMB charter, detailing all aspects of the DSMB's composition, scope of review, and procedures will be provided in a separate document. In addition, the DSMB will review safety data after the first 3 patients enrolled have received their 3rd dose.

An unblinded statistician will be assigned to the DSMB. This statistician will not be involved in any aspects of study conduct outside of the DSMB, and their role will be defined in the DSMB charter.

10.1.6 Dissemination of Clinical Study Data

Data generated by this study must be available for inspection by the FDA, the Sponsor or their designee, applicable foreign health authorities, and the IRB/IEC as appropriate. Patients or their

legal representatives may request their medical information be given to their personal physician or other appropriate medical personnel responsible for their welfare.

Patient medical information obtained during the study is confidential and disclosure to third parties other than those noted above is prohibited.

10.1.7 Data Quality Assurance

- All patient data relating to the study will be recorded on printed or eCRF unless transmitted to the Sponsor or designee electronically (eg, laboratory data). The Investigator is responsible for verifying that data entries are accurate and correct by physically or electronically signing the case report form (CRF).
- The Investigator must permit study-related monitoring, audits, IRB/IEC review, and regulatory agency inspections and provide direct access to source data documents.
- Monitoring details describing strategy (eg, risk-based initiatives in operations and quality such as Risk Management and Mitigation Strategies and Analytical Risk-Based Monitoring), methods, responsibilities and requirements, including handling of noncompliance issues and monitoring techniques (central, remote, or on-site monitoring) are provided in the Monitoring Plan.
- The Sponsor or designee is responsible for the data management of this study including quality checking of the data.
- The Sponsor assumes accountability for actions delegated to other individuals (eg, Contract Research Organizations).
- Records and documents, including signed ICFs, pertaining to the conduct of this study must be retained by the Investigator for 5 years after study completion unless local regulations or institutional policies require a longer retention period. No records may be destroyed during the retention period without the written approval of the Sponsor. No records may be transferred to another location or party without written notification to the Sponsor.

10.1.8 Source Documents

- Source documents provide evidence for the existence of the patient and substantiate the integrity of the data collected. Source documents are filed at the Investigator's site.
- Data reported on the CRF or entered in the eCRF that are transcribed from source documents must be consistent with the source documents or the discrepancies must be explained. The Investigator may need to request previous medical records or transfer records, depending on the study. Also, current medical records must be available.
- The Investigator must maintain accurate documentation (source data) that supports the information entered in the CRF.
- Study monitors will perform ongoing source data verification to confirm that data entered into the CRF by authorized site personnel are accurate, complete, and verifiable from source documents; that the safety and rights of patients are being protected; and that the

study is being conducted in accordance with the currently approved protocol and any other study agreements, ICH GCP, and all applicable regulatory requirements.

